## SECTION 5: INFORMED CONSENT PROCESS

### 1. Methods of Informed Consent

Indicate all applicable informed consent methods for this study. *Submit the consent/assent document(s) with your e-IRB Application (e.g., Study Information Sheet, Recruitment script, Consent Form, etc.). Only IRB approved consent forms (containing the IRB approval footer) may be used to consent human subjects at UCI.*

**Written (signed) informed consent will be obtained from subjects.** Signed informed consent, parental permission, and/or child assent will be obtained from subjects, as applicable.

**Requesting a waiver of written (signed) informed consent.** Signed consent will not be obtained; consent will be obtained verbally or via the web. Informed consent, parental permission and/or child assent will be obtained from subjects, as applicable.

Complete Appendix P.

**Requesting to seek surrogate consent from a legally authorized individual.** Surrogate consent may be considered only in research studies relating to the cognitive impairment, lack of capacity or serious or life-threatening disease and conditions of the research subjects.

Complete Appendix E.

**Requesting a waiver of informed consent.** (i.e., consent will not be obtained). *Skip to Section 5.B.*

Complete Appendix O.

Indicate where the consent process will take place.

In a private room

In a waiting room

In an open unit

In a group setting

The internet

In public setting

Over the phone

Other (specify): At the initial screening, each prospective subject will be given a full explanation of the nature and purpose of the study by qualified staff. The potential subjects are scheduled for 1.5-hour appointments, but they may choose to take the consent home for further review and return to our facility at another appointment time.

3. Specify how the research team will assure that subjects have sufficient time to consider whether to participate in the research.

Subjects will be allowed to take home the unsigned consent form for review prior to signing it.

Subjects will be allowed <Type here> hours to consider whether to consent.

Other (specify): <Type here>

If children are enrolled in this study, describe the parental permission process and the child assent process.

Not applicable: Children are not enrolled in this study.

Once the subjects have been identified as appropriate candidates for this pilot study, the protocol will be explained in detail to the patient and/or if appropriate the parent or legal guardian at a convenient time for the patient/parents by the physician investigators. Subjects will be considered appropriate if they have a skin area of interest for imaging and laser treatment is planned. Consent form, and HIPAA authorization form will be obtained including written UCI assent forms, from eligible infants/children/minor patient consent will be obtained from the patient's parent(s) or legal guardian(s).

Subjects will be informed that their participation in the pilot study is completely voluntary, and that a decision either to participate or not will not affect their care in any way. They will be given as much time as they wish to decide on participation, and will be told that they may discontinue participation at any time. Written consent will be obtained from all populations. Consent Form for Adults and assent for Children ages 13-17, and minor assent forms (ages 4-12 years old) will be obtained. Informed consent form in the way of parental permission will be collected for minors aged 0-3 who cannot yet provide assent. Parent will only be approached about participation in study after birth of their child and not before. This can be feasibly carried out via postnatal permission without compromising study design.

1. Some subjects may be vulnerable to coercion or undue influence, such as those who are economically or educationally disadvantaged, mentally disabled, or students (undergraduate, graduate, and medical students) and employees of UCI (administrative, clerical, nursing, lab technicians, post-doctoral fellows and house staff, etc.), describe the procedures to ensure the voluntary participation of these individuals.

Not applicable: Subjects are not vulnerable to coercion or undue influence.

Other (specify): Please see above explanation regarding children and consent/assent.

## 2. Health Insurance Portability and Accountability Act (HIPAA) Authorization

Indicate all applicable HIPAA authorization methods for this study.

Not applicable: Study does not involve the creation, use, or disclosure of Protected or Personal Health Information (PHI).

**Requesting a Total waiver of HIPAA Authorization.** HIPAA authorization will not be obtained at all for the study.

Complete Appendix T.

**Requesting a Partial waiver of HIPAA Authorization.** HIPAA authorization will not be obtained for screening/recruitment purposes. However, written (signed) HIPAA research authorization is obtained for further access to personal health information.

Complete Appendix T.

**Written (signed) HIPAA Research Authorization will be obtained from subjects.**

Signed authorization, parental authorization, and/or child assent will be obtained from subjects, as applicable.

Complete the HIPAA Research Authorization form.

## 3. Methods of Informed Consent for non-English Speakers

1. Indicate the applicable informed consent method for non-English speakers.

Not applicable: Only individuals who can read and speak English are eligible for this study. *Scientific justification must be provided in Section 3.C.2.*

The English version of the consent form will be translated into appropriate languages for non-English speaking subjects once IRB approval is granted. *The translated consent form must be submitted to the IRB for review prior to use with human subjects. Only IRB approved consent forms (containing the IRB approval stamp) may be used to consent human subjects at UCI.*

Requesting a short form consent process.

Complete Appendix Q.

The short form process will be used for the following occasional and unexpected languages:

All non-English languages

All non-English languages except Spanish

Other languages (specify): <Type here>

Explain how non-English speaking subjects will be consented in their language and who will be responsible for interpreting and facilitating the informed consent discussion for the non-English speaking subjects.

At least one member of the study team is fluent in the language that will be used for communication, and that study team member(s) will be available during emergencies.

*For all members of the study team responsible for obtaining informed consent from non-English speaking subjects, provide their qualifications to serve in this capacity (i.e. language fluency) in Section 2.*

The study team has 24-hour access to a translation service with sufficient medical expertise to discuss the research in this study.

Other (explain): <Type here>

## **SECTION 6: RESEARCH METHODOLOGY/STUDY PROCEDURES**

### **1. Study Location**

Specify where the research procedures will take place (e.g. UCI Douglas Hospital – Cardiac Care Unit, UCI Main Campus Hewitt Hall, UCI Health – Pavilion II, UCI Family Health Center, Anaheim, Irvine High School).

*If research activities will also be conducted at non-UCI locations (e.g., educational institutions, businesses, organizations, etc.), Complete Appendix A. Letters of Permission or other documentation may be required (e.g. Off-site Research Agreements or IRB Authorization Agreements).*

Subjects will be recruited from patients seen in the Department of Dermatology clinics at the University of California Irvine (UCI). After explaining the nature, rationale, objectives, benefits, and risks of the pilot study to the patients, they will be asked to consent to the study. Patients who agree to participate will sign an informed consent form before their enrollment into the study.

### **2. Study Design**

Include an explanation of the study design (e.g., randomized placebo-controlled, cross-over, cross-sectional, longitudinal, etc.) and, if appropriate, describe stratification/ randomization/blinding scheme.

This is a longitudinal study with matched prospective controls. The patients will undergo treatment and follow-up over the course of 1-7 months. Their results will be compared to that of matched prospective controls with similar treatment and follow duration. There is no placebo, and patients will not be blinded.

Patients will be stratified based on their lesion type and the size of the lesion as these factors may impact the response to laser treatment and thus the data measurements from OCT. Photographs of the patients' treated lesions will be rated for lesion improvement by blinded physicians. OCT measurements of the lesion of interest will be used to validate the improvement and cosmetic results.

Provide precise definitions of the study endpoints and criteria for evaluation; if the primary outcomes are derived from several measurements (i.e., composite variables) or if endpoints are based composite variables, then describe precisely how the composite variables are derived.

Primary endpoints include photographic improvement of the lesion(s) of interest after 1 or more laser treatments. Two board certified dermatologists grade the degree of improvement (clearance of the lesion) in quartiles (no clearance=0-25, mild clearance=26-50, good clearance=51-75, excellent clearance=76-95, complete clearance=96-100). It will be up to the experienced treating dermatologist to determine the number of treatments necessary for maximum clearance of the lesion(s).

Secondary endpoints include measurements with OCT, which show reduced lesion thickness, lesion size, size of blood vessels, and density of blood vessels, and number of superficial blood vessels.

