**Originally collected for research purposes:**

NO – Please explain: [<Type here>](#)

YES – UCI IRB approval granted under IRB protocol number (i.e. HS#): [<Type here>](#)

YES – Non-UCI IRB approval granted. Confirm one of the following:

A copy of the IRB Approval Notice and Consent Form for the original research collection will be submitted with the IRB application (APP). The IRB Approved Consent Form does not preclude the proposed activity.

A copy of the commercial Vendor Policy or a Letter from the Vendor attesting that the information was collected and will be shared in an appropriate and ethical manner will be submitted with the APP. The vendor's policy does not preclude the proposed activity.

5. Provide a complete list of the **data points, variables, and/or information** that will be collected **during the screening process** (i.e. data abstraction form). *Note: Only the minimum information necessary to determine subject eligibility should be collected during the screening process.*

For the experimental group, we would screen for the patient's age, type of lesion/diagnosis, location of the lesion, and the patient's willingness and ability to participate in the study.

For the control group, we would screen for the patient's age, type of lesion/diagnosis, location of the lesion, and the clearance of the lesion and response to treatment.

Check here if the list is submitted as a separate document with the application.

6. Specify what will happen to the information and/or biospecimens, if the potential subject is not eligible to participate in the study. *Note: Information or biospecimens of non-eligible subjects, may not be included as part of data analysis or disclosed beyond the study.*

The study team plans to destroy the identifiable information and/or biospecimens at the earliest opportunity consistent with conduct of the research. Describe the protocol specific plan and timeframe for destruction: [<Type here>](#)

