Some subjects may be asked to participate in more than one imaging session. They will have the option of refusing participation in additional sessions. Follow-up examinations will be performed every 4 weeks. During these examinations, photography and imaging of the lesion of interest will be performed with optional laser treatments to be performed at the discretion of the treating physician and the patient. If no laser treatment is necessary, then the visit should take no more than 30 minutes for a quick follow-up and imaging. Additional laser treatment will require no more than 30 minutes to complete. The number of follow-ups is also determined at the discretion of the treating physician and the patient but could range from 1 to 6 depending on the response of the lesion to treatment.

Matched prospective controls will be gathered to be compared against the imaged, treated, experimental group. The prospective controls will be matched to age, gender, skin type, and type of skin lesion. They will be gathered via a retrospective chart review by abstracting and data directly from our own records.

Describe the duration of a subject's participation in the study. If there are sub-studies, include duration of participation in each sub-study.

For each visit: history and skin examination-30 minutes, imaging – up to 30 mins, and laser treatment – up to 30 mins. These are all maximums and will likely be shorter.

At a follow-up, the patient may or may not receive a laser treatment thus shortening the visit. A patient would be expected to have 1-6 follow ups depending on their response to treatment, so their maximum time in this study could range from about 1 to 6 months. Each follow-up visit is made about 4 weeks from the prior visit.

List data collection instruments (e.g., measures, questionnaires, interview questions, observational tool, etc.).

*Investigator-authored, non-standardized, or un-validated measures must be submitted for review.*

Standardized photography,  
OCT

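### Choosing controls for similar treatment and follow-up duration selects them on a consequence of response, and may shrink the powered first-treatment difference by an amount the documents do not fix

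*Combined protocol and SAP*

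**What the plan says.** Four parts of the combined protocol and SAP bear on this.

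- **Control group (Section 6, Study Design).** The OCT patients are treated and followed for 1 to 7 months, and "Their results will be compared to that of matched prospective controls with similar treatment and follow duration". No tolerance or unit is given for similarity. The same section stratifies by lesion type and lesion size because these may affect response.
- **Length of course (Section 6, Study Design and Research Procedures).** The treating dermatologist decides how many treatments are needed to reach maximum clearance. The number of follow-ups is at the discretion of physician and patient and "could range from 1 to 6 depending on the response of the lesion to treatment". The paragraph on duration of participation repeats this: "A patient would be expected to have 1-6 follow ups depending on their response to treatment".
- **Selection of controls (Section 6, Research Procedures; Section 3, screening data).** "The prospective controls will be matched to age, gender, skin type, and type of skin lesion". Duration is not in this list. The next sentence reads: "They will be gathered via a retrospective chart review by abstracting and data directly from our own records". The data screened for controls include "the clearance of the lesion and response to treatment".
- **Endpoint and analysis (Section 6, Study Design and Statistical Considerations).** "Primary endpoints include photographic improvement of the lesion(s) of interest after 1 or more laser treatments". The analysis is a two-sample t-test at each treatment. The sample size rests on clearance after one treatment: 60% with imaging against 40% without, SD 20, 17 per group.

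**The concern.** Treatment and follow-up duration is not a baseline feature here. By the plan's own account it follows from response, and response is what the primary endpoint grades. If OCT guidance clears lesions faster, OCT patients will tend to need fewer sessions. A control picked because he or she also needed few sessions will tend to be a better-than-average responder to unguided laser. The comparison then sets typical OCT patients against selected controls.

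The selection acts on who enters the control group, so testing separately at each treatment does not remove it; the comparison after treatment 1 is affected too. It also does not require anyone to look at a clearance grade, because the length of the course already carries that information. And if a gain from guidance is fewer sessions, equalising sessions hides it.

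Controls are not randomised, so the selection rule carries much of the weight of the primary comparison.

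**Working it through.** **1. The plan's own figure.** Inputs from Sample Size Determination: difference 20 points, SD 20 per group, two-sided 5%, 80% power. The normal approximation gives n = 2 × (1.96 + 0.84)² × (20/20)² = 15.7, so 16 per group. With the exact noncentral t distribution, power is 0.781 at 16 and 0.807 at 17 per group. The stated 17 per group reproduces.

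**2. Reserve.** With n = 17 the noncentrality is difference / (20 × √(2/17)) on 32 degrees of freedom.

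| Difference | Noncentrality | Power |
|---|---|---|
| 20 | 2.92 | 0.81 |
| 15 | 2.19 | 0.56 |
| 10 | 1.46 | 0.29 |

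**3. Simple model of duration matching.** Let Y be clearance after treatment 1, and let a response index D = Y + error determine duration, with within-group correlation ρ between D and Y. The slope of Y on D is then ρ². Among patients with equal D, the group difference in Y is 20 − ρ² × 20 = 20 × (1 − ρ²). The documents give no ρ; the values below are assumptions, and SD is held at 20.

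| ρ | Difference left | Power, 17 per group |
|---|---|---|
| 0 | 20.0 | 0.81 |
| 0.3 | 20 × 0.91 = 18.2 | 0.73 |
| 0.5 | 20 × 0.75 = 15.0 | 0.56 |
| 0.7 | 20 × 0.51 = 10.2 | 0.30 |
| 0.8 | 20 × 0.36 = 7.2 | 0.18 |

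In this model a true difference of zero stays zero, so the distortion is a loss of effect, not a false gain.

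**4. Simulated courses of treatment.** Treatment-1 clearance had means 60 and 40, with up to 7 treatments. Controls were matched exactly on number of treatments. Without matching, the first-treatment difference was about 19.7 points (slightly under 20 because clearance is bounded at 0 and 100). The stopping rules are assumptions.

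| Stopping rule | Points left | Share of about 19.7 |
|---|---|---|
| Clearance threshold 75 or 95, no judgement error | 1.3 to 4.2 | 6 to 21% |
| Same, judgement error SD 10 | 4.9 to 10.2 | 25 to 52% |
| Same, judgement error SD 20 | 9.3 to 13.2 | 47 to 67% |
| Same, judgement error SD 40 | 14.4 to 16.5 | 73 to 84% |
| Plateau: stop when the last gain is below 5 or 10 points | 13.3 or 16.3 | about 68 or 83% |
| Threshold 75 plus 20% or 40% discretionary stopping per visit | 15.7 or 18.5 | about 80 or 94% |

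Repeat runs with somewhat different response models gave about 0 to 5 points under strict thresholds and up to 19.6 points under plateau or discretionary stopping. Matching within one treatment, under the threshold rules with and without judgement error, kept 24 to 90%. The first-treatment difference moved toward zero in every run, in some of them hardly at all.

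**5. End-of-course clearance.** Under the threshold rules the unmatched difference is already small (1.5 to 12.4 points), because both groups are treated toward maximum clearance. Matching moved it both ways: from 4.6 to 0.8 points in one run (threshold 95, no error) and from 6.0 to 11.4 in another (threshold 75, error SD 20).

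**The case against.** The strongest reply is that duration may not be a selection criterion at all. The sentence in Study Design is an overview. It can be read as saying that, as a group, controls had similar laser treatment over a similar window. The only explicit list of matching variables leaves duration out. This stands in part: a reader might infer that the plan definitely matches on duration, and the documents do not settle that. But nothing says that the list overrides the overview, and chart review makes the broader reading workable. The conflict is itself something to resolve.

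A second reply concerns size. A reader might infer that the criterion cancels most of the effect. That follows only if treatment stops strictly at a fixed clearance threshold. The plan describes treatment toward maximum clearance, closer to a plateau, where poor responders may also stop early. It leaves further sessions to physician and patient, and patients or insurers pay for them. All of this loosens the tie between duration and response. Rules nearer the text keep most of the 20 points, so a near-total loss is not established.

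A third reply concerns direction. A reader might infer bias toward no difference throughout. The calculations support that for the comparison after treatment 1, not for end-of-course clearance. This objection stands.

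A last point is that patients with similar exposure are fairer to compare. A fixed assessment point achieves that without selecting on response.

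**Conclusion.** The concern holds in a limited form. If similar treatment and follow-up duration is applied as a control criterion, controls are selected on a consequence of the outcome, and the powered first-treatment comparison is biased toward no difference when OCT guidance works. The documents do not fix the size. Under the assumed stopping rules and exact matching on number of treatments, the loss runs from almost none to more than 80% of the planned 20 points. A loss of one quarter would already take power from 0.81 to 0.56. These figures assume SD 20 after selection and that guidance affects duration through response.

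It would go too far to say that a null result could not be interpreted at all, since that depends on how strictly similarity is applied and how closely duration tracks response. For a pilot study with an unquantified phrase and a conflicting matching list, this should be fixed before controls are selected, but it is not shown to defeat the design.

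**What to change.** 1. In Study Design, remove similar treatment and follow-up duration as a condition on controls, so that the section agrees with the matching list in Research Procedures.
2. Match only on features fixed before the first treatment: age, gender, skin type and lesion type, as already listed, plus lesion size, which Study Design itself names as possibly affecting response.
3. Require of a control only what the outcome needs: a pre-treatment photograph and one at the follow-up after treatment 1.
4. Make the comparison after treatment 1, on which the sample size already rests, the main one. Keep the later at-each-treatment comparisons as descriptive.
5. Report number of treatments as an outcome in both groups.

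None of this changes how patients are treated or who decides the number of sessions. The cost is more than deleting one phrase: the endpoint and analysis text must also name the main time point. The groups may differ in total sessions, and fewer controls may contribute to later-treatment comparisons, so those results must be described with that limit. Adding lesion size may make matches harder to find.

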### 3. Research Procedures

Provide a detailed chronological description of all research procedures.

A screening log of all potential subjects will be kept at our site. All screening evaluations must be reviewed by the investigator to establish patient eligibility prior to registering the patient for this study.

The following screening evaluation should be completed for all subjects on the first visit:

- Informed consent and photograph release form
- Focused medical history including diagnosis of lesion if applicable. This includes general questioning about the patient's health, well-being, allergies, and medications, and history of the skin lesion in question as identified by the patient and confirmed by the physician.
- Focused skin exam. This includes a detailed medical examination of the skin lesion in question.
- Documentation of area of skin to be studied. This will be determined by the patient's indication and confirmed by the physician.

On visit number one of the study, patients will consent to the study, and an area of skin to be studied will be photographed by digital photography. If the study area is on the face, subjects will be offered to protect their identity.

Non-invasive imaging will then be performed with OCT. Each individual scan with OCT takes about 30 seconds to complete, and we may perform multiple scans on larger lesions. Based on the data and information obtained, the appropriate laser device and settings will be applied for the most optimal treatment to achieve the best results with the fewest side effects. Then laser treatment will be performed on the lesion of interest. Immediate post-treatment imaging and photography will be conducted to assess the results of the treatment. This first visit should take no more than 1.5 hours: approximately 20 minutes for a medical history and focused skin examination, 30 minutes for imaging including photographs, and 30 minutes for laser treatment. These times are all maximums and will likely be shorter. The patient may take as long as needed to consent and is permitted to take the consent form home and return another day to sign and enroll.

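### Controls can be chosen with their outcome already known, and the plan does not secure comparable, group-masked photograph grading for controls drawn from charts

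*Combined protocol and SAP*

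**What the plan says.** **Outcome and blinding.** Section 6, Study Design, defines the primary endpoint as photographic improvement: "Two board certified dermatologists grade the degree of improvement (clearance of the lesion) in quartiles". It adds that photographs of the patients' "treated lesions will be rated for lesion improvement by blinded physicians". It does not say what the raters are blinded to, or how. Of the patients it says: "There is no placebo, and patients will not be blinded".

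**Photographs.** Under Research Procedures, at visit 1 "an area of skin to be studied will be photographed by digital photography". OCT and laser treatment follow, with more photography immediately afterwards. At the four-weekly follow-ups "photography and imaging of the lesion of interest will be performed". The list of data collection instruments names "Standardized photography" and OCT, without assigning either to a group. The section on collection of photographs says that names are not used and eyes are hidden when photographs are evaluated. It says nothing about hiding group or date.

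**Controls.** Section 1, the enrolment table in Section 3, Study Design, Research Procedures and the sample size text all call the controls prospective. Research Procedures then says: "They will be gathered via a retrospective chart review by abstracting and data directly from our own records". The Statistical Analysis Plan describes them as patients treated conventionally in the past, while still calling them a prospective control.

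**Screening.** Section 3, Screening and Determining Eligibility, item 5, has a separate list for each group. Both include age, lesion type and lesion location. The OCT list adds willingness and ability to take part. The control list adds "the clearance of the lesion and response to treatment".

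**The concern.** The primary analysis compares a subjective grade between two non-randomised groups, so its validity depends on how controls are chosen and on both groups being graded in the same way.

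On the first, whoever applies the control screening list sees how each candidate responded before deciding on inclusion. Matching on age, gender, skin type and lesion type still leaves a choice among several eligible records, and knowledge of the outcome can influence that choice without any intent.

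On the second, if controls are past patients, the study cannot prescribe their photographs. Whatever exists in the chart may differ in timing and conditions from the OCT group's photographs, and those differences could tell a grader which group a picture belongs to. A shift from either source is fully confounded with group, and no later analysis can separate it from an effect of OCT guidance.

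**Working it through.** **Step 1. Set the passages side by side.**

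| Item | OCT group | Controls |
|---|---|---|
| Source | Enrolled at visit 1 | Labelled prospective; gathered by chart review; past patients in the Statistical Analysis Plan |
| Outcome in screening list | No | Yes: clearance and response |
| Scheduled photographs | Visit 1 before and after treatment, then every 4 weeks | None described |
| Who grades | Two board certified dermatologists | Not stated separately |
| Masking of photographs | Name and eyes | Nothing further stated |

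The second row is an explicit rule in the protocol. The other control entries are either contradictory (source) or unspecified (photographs, grading).

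**Step 2. Reproduce the plan's sample size.** Inputs from Sample Size Determination: means 60 and 40, SD 20 in each group (reading ±20% as an SD), two-sided two-sample t test at 5%, 17 per group, 80% power.

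- Standard error = 20 × √(2/17) = 6.86 points.
- Noncentrality = 20 / 6.86 = 2.915, with 32 degrees of freedom and critical value 2.037.
- Power = P(|T| > 2.037) for noncentral T = 80.7%. With 16 per group it is 78.1%.

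The plan's 17 per group is confirmed and is not in dispute.

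**Step 3. Illustrate a systematic shift between groups.** The documents give neither size nor direction, so shifts of 5 and 10 points are assumed. A shift b adds to the true difference d, and the noncentrality becomes (d + b) / 6.86. The arithmetic is the same whether b comes from selection or from grading, provided the SD stays at 20.

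| True difference | Shift | Net difference | Noncentrality | P(p<0.05, two-sided) |
|---|---|---|---|---|
| 0 | 0 | 0 | 0 | 5.0% |
| 0 | 5, either direction | 5 | 0.729 | 10.9% |
| 0 | 10, either direction | 10 | 1.458 | 29.3% |
| 20 | 0 | 20 | 2.915 | 80.7% |
| 20 | 5 against OCT | 15 | 2.187 | 56.4% |
| 20 | 10 against OCT | 10 | 1.458 | 29.3% |

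The width of the grading bands neither estimates nor bounds such a shift, so it is not used as an anchor.

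**The case against.** The strongest reply is that a reader might infer more than the documents say.

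- **That the primary outcome is measured differently in the two groups.** The documents do not support this as a fact. They define one primary outcome, the dermatologists' photograph grade. Nothing lets clearance recorded in the chart replace it, and nothing limits standardized photography to the OCT group. Study Design asks for similar treatment and follow-up duration in controls. The first-visit list, including the photograph release, is written for all subjects. Section 11 says that photographs are captured through the medical record application, so a difference in format from chart photographs cannot be presumed.
- **That the graders have already seen the recorded clearance.** This is not stated either. The screening list concerns those who select controls. It would compromise the graders' blinding only if the same people did both, which the plan neither says nor excludes.
- **That the controls are simply historical.** The text contradicts itself. If controls were enrolled prospectively, much of the doubt about photographs would fall away.

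These points rule out the stronger readings and leave a narrower point standing. The outcome items are in the control screening list under any reading. The only description of how controls are obtained is chart review. Listing standardized photography as an instrument cannot standardize pictures already taken. Even with prospective controls, the described photography visits are built around OCT imaging, which controls do not receive, so their photograph schedule would still need to be written down.

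**Conclusion.** The concern holds in two parts of unequal strength. The firm part is selection: the protocol allows controls to be chosen with clearance and response in view, and applies no such item to the OCT group. The weaker part is assessment: under chart review, comparable grading masked to group is doubtful because control photographs, their timing and the masking of group and date are unspecified. The documents do not show that grading actually differs.

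Neither the size nor the direction of any bias can be derived from the documents. The illustration rests on assumed shifts, an SD of 20, 17 per group and clearance treated as a percentage. On those terms, a 5-point shift roughly doubles the false-positive rate, or takes power from 80.7% to 56.4% if it runs against OCT. The change should be made before any control is selected, because the data cannot show afterwards whether it was needed.

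**What to change.** 1. Reconcile the passages on the control source, so that the design, procedures, enrolment table and analysis text all describe the same controls.
2. Remove clearance and response from the control screening list, and state that controls are selected and matched without knowledge of outcome.
3. Require for each control a pre-treatment photograph and a post-treatment photograph in the same window as the OCT group's photograph at the analysed timepoint.
4. Have the same two dermatologists, who take no part in selecting controls, grade all photograph pairs from both groups in one randomly ordered set, cropped to the lesion, with dates and group removed. Use only that grade as the primary outcome in both groups.

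The cost is protocol wording and some image preparation. No extra graders are needed, provided the two named for grading are not the people selecting controls. The main downside is the loss of controls without suitable photographs. The enrolment table allows up to 30 controls for the 17 needed, a margin of 13, but that maximum includes withdrawals and screen failures, controls must also match on four factors, and photograph availability is unknown. A count of usable chart photographs before finalising the wording would settle whether the margin is enough.
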